4 STUDY DESIGN

This Phase 1/2 study will utilize a multicenter, open-label, dose-escalation design to evaluate the safety, efficacy, PK, and PD of FT-2102 administered orally to patients with AML or MDS.

Patients will be given FT-2102 daily (QD or BID) in continuous 28-day cycles, alone or in combination with azacitidine (administered at the dose of 75 mg/m² for 7 days IV/SC per every 28-day cycle) or LDAC (administered at the dose of 20 mg BID SC for 10 days every 28-day cycle) until treatment discontinuation. The term "study drug" will refer to either FT-2102, azacitidine or cytarabine.

Patients who discontinue for reasons other than disease progression/relapse or withdrawal of consent will continue to be followed for response until progression/relapse occurs.

Patients who achieve an adequate response to study treatment and meet other criteria required to undergo hematopoietic stem cell transplantation (HSCT) may proceed to HSCT after discontinuation of study treatment and will be followed on study for disease evaluation and any new HSCT conditioning or other new antineoplastic therapies received until disease relapse, death, withdrawal of consent, lost to follow-up, or end of study.

If a patient discontinues study drug to undergo HSCT, but is then deemed ineligible for HSCT, the patient may restart study drug with Medical Monitor approval.

Patients who undergo HSCT and then have persistent/recurrent IDH1-mutant (IDH1m) positive disease may be eligible to restart treatment with FT-2102 by re-enrolling in the appropriate Phase 2 cohort with Medical Monitor approval:

• Re-enrollment into Cohort 3 if morphologic relapse/progression

Patients who relapse post-HSCT and elect not to restart FT-2102 treatment will enter the overall survival follow-up period.

[figure not shown]
Patients participating in Phase 1 may be followed for survival for up to 12 months from C1D1 or for 28 days after treatment discontinuation (whichever is longer).

Patients participating in Phase 2 may be followed for survival for up to 36 months from C1D1 or for 28 days after treatment discontinuation (whichever is longer).

As shown in Figure 1, the study is comprised of 3 stages: a Phase 1 dose-escalation stage, a Phase 1 dose-expansion stage, and a Phase 2 stage.

Figure 1 Study Design

Phase 1 – Dose Escalation and Dose Expansion

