7.2 Reporting of Adverse Events

7.2.1 Adverse Events

Refer to Section 6.2.1 for a summary of ongoing safety review during the study, including review of any new Suspected Unexpected Serious Adverse Reactions (SUSARs).

Serious AEs (SAEs) will be collected from the time the patient signs the informed consent form until 28 days after the last dose of study drug, or until the initiation of an investigational agent or cytotoxic chemotherapy, whichever comes first, and as per Section 7.2.3. Serious AEs will be collected on the Adverse Event eCRF from the time of first dose of study drug until 28 days after the last dose of study drug, or until the initiation of an investigational agent or cytotoxic chemotherapy, whichever comes first.

Adverse Events of Special Interest (AESI), as defined in Section 7.2.4, should be collected on the AESI Form from the time of first dose of study drug until 28 days after the last dose of study drug and reported to Forma Therapeutics Pharmacovigilance within 24 hours of knowledge of event.

Non-serious adverse events will be collected and reported on the Adverse Event eCRF from the time of the first dose of study drug until 28 days after the last dose of study drug, or until the initiation of an investigational agent or cytotoxic chemotherapy, whichever comes first.

Patients withdrawn from the study because of AEs will be followed by the Investigator until the outcome is determined. When appropriate, additional written reports and documentation will be provided.

All AEs beginning after the last exposure of study drug must be reported to the Sponsor or its designee if the onset of the AE was within 28 days of the last exposure to study drug. All AEs, whether serious or nonserious, that are judged by the Investigator to be at least possibly related to study drug administration must be reported to the Sponsor or its designee regardless of how much time has elapsed since the last exposure to study drug (i.e., beyond 28 days of the last exposure to study drug).

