Seven analysis sets are defined for use in various analyses. The following table illustrates the relationship between each analysis set and the analyses. Within an analysis set, the summary table will summarize data within cohorts, as described in Appendix 3. Due to the large number of cohorts in this study (there are eight Phase 2 cohorts), individual cohorts do not have their own analysis set; the result for a hypothesis being tested on a single cohort is found in the summary table for the applicable analysis set, within the table column that describes patients in the applicable cohort.

			Analys	sis			
Analysis Set	Patient	Patient					DLT
	Characteristics	Disposition	Efficacy	Safety	PK	PD	Evaluation
DLT Evaluable Set							Χ
Safety Analysis Set		X		X			
Efficacy Evaluable	v		v				
Analysis Set	Λ		Λ				
Full Analysis Set	X	X	X				
Per Protocol			X				
Analysis Set							
PK Analysis Set					Χ		
PD Analysis Set						Χ	

1. DLT Evaluable Set

All Phase 1 patients who enrolled in the dose escalation cohorts and who have received at least one dose of FT-2102 and completed at least 75% of doses in the first cycle during the DLT evaluation period or have discontinued / interrupted due to adverse events meeting the DLT evaluation criteria. This set will be used for DLT analyses only, unless otherwise specified.

2. Safety Analysis Set

All patients who have received at least one dose of study drug (FT-2102, azacitidine, or cytarabine). All safety analyses will be based on the Safety analysis set unless otherwise specified. Patients will be analyzed under the first dose level received by the patient.

3. Full Analysis Set (FAS)

All patients who were enrolled in the study and have received at least one dose of FT-2102. This analysis set will be used for efficacy analyses and baseline characteristics. Patients will be analyzed under the assigned dose.

4. Efficacy Evaluable (EE) Analysis Set

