Adverse Events (AEs) will be summarized and recorded from the time of first dose through 28 days after the last dose of study drug, and serious adverse events from the time of informed consent to 28 days after the last dose of study drug. AEs will be coded using the MedDRA dictionary version 19.1, with verbatim terms coded by System Organ Class (SOC) and Preferred Term (PT) and graded via the CTCAE version 4.03. Sponsor coding conventions will be applied during the creation of analysis datasets. Therefore, the raw dataset may reflect a different preferred term than the ADAE data set.

A treatment-emergent AE (TEAE) is an AE that emerges after the first dose of study drug through 28 days post last dose, having been absent pretreatment, that occurred on or after the first dose of study treatment or within 28 days after the last dose, or occurred prior to the first dose and increased in grade during study treatment. If an AE has partial onset date, the imputed onset date as specified in Section VI.C will be used to define TEAE.

The causality of an AE includes related or unrelated. A treatment-related AE is defined as an AE considered "Possibly Related", "Probably Related", or "Definitely Related" to the study drug by the investigator. Missing relationship will be treated as unknown and excluded from summary of treatment-related AEs considered to be related; events reported as "Definitely Not Related", "Probably Not Related", or "Unlikely" will be considered not related.

If the AE start or stop date is still missing after implementing the rules specified in Section VI.C, the following strategy will be used to determine whether AEs with missing start or stop dates are pre-treatment or treatment-emergent:

- 1. If the start date and stop date are both missing, the most conservative approach is taken, and the AE is considered to be treatment-emergent.
- 2. If the start date is missing but the stop date is not missing and is after the day of study dose administration, then the most conservative approach is taken, and the AE is considered to be treatment-emergent.
- 3. If the start date is missing but the stop date is not missing and is on or before the day of study dose and after the date of signed informed consent, then the AE is considered to be pre-treatment (not TEAE).

The following AE summaries will be produced for both Phase 1 and 2:

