For a patient with none of these events before the end of study follow-up, EFS will be censored as per Table 1. For patients lost to follow-up prior to any evidence of event, the EFS data will be censored at their last completed assessment date that is SD or better prior to the initiation of anti-cancer therapy.

Overall survival (OS): OS is defined as the time in months from the first dose of study drug until death from any cause. For patients who are not known to have died by the end of study follow-up, OS will be censored on the date the patient was last known to be alive.

Transfusion independence (TI): Patients will be classified as "dependent" or "independent" at baseline within each category of platelets, pRBC, any (i.e., receiving either platelets or pRBC or both) and both (i.e., receiving both platelets and pRBC) if they received a transfusion within 8 weeks prior to the first dose of FT-2102. TI will be defined as patients who experience at least a 28-day or 56-day period during any point on treatment with no transfusion of that type required. For the "both" category, patients who are classified as dependent must have received both a platelet and pRBC transfusion within the 8 weeks prior to baseline, and to be classified post baseline as independent, they must experience a 28 or 56 day minimum duration on study where they did not require a transfusion of either platelets or pRBC.

B. Efficacy Analysis

Any response assessment occurring after the start of alternate anti-cancer therapy will not be included in the analyses using response assessments.

Note that some patients who were assigned to single agent therapy in Phase 1 requested to start combination therapy with azacitidine when a response was not observed on single agent treatment. In such cases, upon beginning dosing with azacitidine (if the patient was assigned to single agent therapy), then response assessments occurring after the first dose of azacitidine will not be included in efficacy analyses. Time to event analyses for such instances will be treated as if the patient has experienced disease progression when azacitidine is initiated.

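### Efficacy for Phase 1 single-agent patients who added azacitidine stops at the first azacitidine dose, but safety does not, so combination-period events are tabulated in the single-agent columns

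*SAP*

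**What the plan says.** SAP section XI.B (Efficacy Analysis) notes that "some patients who were assigned to single agent therapy in Phase 1 requested to start combination therapy with azacitidine" when no response was seen on the single agent. For them, "response assessments occurring after the first dose of azacitidine will not be included in efficacy analyses". It adds: "Time to event analyses for such instances will be treated as if the patient has experienced disease progression when azacitidine is initiated". Table 1 in the same section instead censors such patients at the last adequate assessment before combination therapy. The two time-to-event rules conflict and need reconciling as a separate matter, but both end single-agent follow-up at the switch.

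The safety sections say nothing about the switch:

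- Attribution (SAP VI.I, Safety Analysis Set): "Patients will be analyzed under the first dose level received by the patient".
- Event window (SAP VIII.B): "A treatment-emergent AE (TEAE) is an AE that emerges after the first dose of study drug through 28 days post last dose". Protocol section 4 says that the term study drug "will refer to either FT-2102, azacitidine or cytarabine".
- Laboratory data (SAP VIII.C): shift tables use the highest CTCAE grade on study.
- ECG (SAP VIII.E): QTcF categories count values at any time during the study, and the shift table uses the maximum post-baseline event.
- Exposure (SAP VIII.A): treatment duration runs from first to last dose.

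SAP Appendix 3 has no column for patients who moved from single agent to combination.

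**The concern.** Adverse events, laboratory abnormalities and ECG changes are the Phase 1 primary endpoint (protocol section 3; SAP III.A). The plan accepts, for efficacy, that what happens after azacitidine starts no longer describes single-agent FT-2102. For safety it makes no such distinction. A cytopenia, an episode of febrile neutropenia or a death during the combination period would be shown under single-agent FT-2102, and a reader of the table could not tell it from an event on FT-2102 alone. At stake is whether the single-agent safety profile describes the regimen named in the column header.

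**Working it through.** The documents give no figure for this point, so the check has two parts: tracing one patient through the rules, then bounding the effect.

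**Tracing a switcher.** Take a patient assigned to single-agent FT-2102 who adds azacitidine after non-response and has a first Grade 4 neutropenia a month later.

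| Rule | Result for this patient |
|---|---|
| SAP XI.B, response | Assessments after the first azacitidine dose are dropped |
| SAP XI.B and Table 1, time to event | Event at, or censoring before, the switch |
| SAP VI.I, Safety Set | Stays under the first dose level, i.e. single agent |
| SAP VIII.B, TEAE | Neutropenia falls inside the window and is counted |
| SAP VIII.C, laboratory shift | Grade 4 becomes the worst grade on study |
| SAP Appendix 3 | Shown in the Phase 1 single-agent columns |

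The result does not depend on how study drug is read. If it includes azacitidine, as protocol section 4 says, the window runs through azacitidine dosing. If it meant FT-2102 only, the patient is still taking FT-2102 as part of the combination, so the window still covers the event.

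Appendix 3 also has a Phase 2 safety column, under a 150 mg BID header, that pools Phase 1 relapsed/refractory AML with Phase 2 Cohort 1. A switcher who fits that description can enter it.

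**Upper bound per switcher.** The number of Phase 1 single-agent patients is not stated, so it is assumed. SAP V.A lists four single-agent levels: 150 mg QD, 300 mg QD, 150 mg BID and a 100 mg QD food-effect cohort. SAP IV.C uses 6 patients per level for planning, and SAP IV.A allows 2 single-agent expansion cohorts of up to 14.

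- Four levels: 4 × 6 + 2 × 14 = 24 + 28 = 52; 1/52 = 1.9 points per switcher.
- Two levels only (150 and 300 mg QD, the planned minimum): 2 × 6 + 28 = 40; 1/40 = 2.5 points.
- Pooled column: about 190 Cohort 1 patients plus the Phase 1 patients; below 1/190 = 0.5 points.

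| Switchers (assumed) | n = 52 | n = 40 |
|---|---|---|
| 2 | 3.8 points | 5 points |
| 4 | 7.7 points | 10 points |
| 8 | 15.4 points | 20 points |

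These are ceilings. They require every switcher to have a first event of the same type, and only after azacitidine starts.

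**A less extreme illustration.** Let p be the incidence on single agent alone, c the share who switch, and q the chance of a first such event after the switch. The tabulated incidence is p + c(1 − p)q. None of the three is in the documents. With p = 10%:

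- c = 5%, q = 20%: 0.10 + 0.05 × 0.90 × 0.20 = 10.9%
- c = 10%, q = 40%: 0.10 + 0.10 × 0.90 × 0.40 = 13.6%
- c = 20%, q = 40%: 0.10 + 0.20 × 0.90 × 0.40 = 17.2%
- c = 30%, q = 60%: 0.10 + 0.30 × 0.90 × 0.60 = 26.2%

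The effect runs from negligible to material depending on c and q.

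**The case against.** Keeping all on-treatment events under the initial group is a recognised conservative convention for safety, and switchers are still taking FT-2102. Protocol 9.2.4.2 presents relationship by study drug where applicable, and SAP VIII.B lists all adverse events by patient, so the events can be found. This part stands as an argument for keeping the uncut tables. It does not answer the point: causality by drug affects only the related-event tables, the SAP's own definition of treatment-related does not separate the drugs, and the all-causality, laboratory and ECG summaries are unchanged.

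Four stronger readings are tempting, and the documents do not support them.

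- **That the gap narrows a planned contrast between single agent and combination.** Safety analyses are descriptive, nothing is randomised, and no formal comparison is planned. Nor is the movement all one way: protocol 4.1.2 and 6.8.3 let combination patients stop azacitidine after the first cycle and continue FT-2102 alone, and they stay in the combination column. That dilutes the combination column but brings in no drug that its header does not name.
- **That a similar gap exists after treatment ends, when salvage or conditioning starts.** Protocol 7.2.1 ends eCRF collection of both serious and non-serious events at "until 28 days after the last dose of study drug, or until the initiation of an investigational agent or cytotoxic chemotherapy, whichever comes first". Only the separate AESI form lacks that stop, and SAP VIII.B builds the hepatic AESI tables from adverse-event preferred terms. Wider reporting duties to the sponsor exist, but nothing says that those reports feed the TEAE tables.
- **That protocol 7.2.1 already cuts safety at azacitidine.** It does not name azacitidine, which the protocol defines as study drug, and it does not govern the laboratory or ECG summaries.
- **That dose selection is compromised.** DLTs are confined to Cycle 1. The switch followed non-response, and the first scheduled marrow assessment is at Cycle 2 Day 1 or Cycle 3 Day 1.

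**Conclusion.** The asymmetry is plain in the text: single-agent efficacy ends at the first azacitidine dose, and single-agent safety does not. Followed as written, the plan tabulates FT-2102 plus azacitidine events in the Phase 1 single-agent columns for a primary endpoint, and can carry some into the pooled column with Cohort 1. How much this changes any rate is not known, because the documents say only that some patients switched. The ceiling is about 1.9 points per switcher for a given event, assuming 52 patients, or 2.5 assuming 40, and about 0.5 or less in the pooled column. It would be wrong to infer that single-agent toxicity has been shown to be inflated. What is established is that the tables would not let a reader tell. DLT and MTD conclusions are largely unaffected. The change is worth making because it is cheap and loses no data.

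**What to change.** In SAP section VIII:

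1. State the number of Phase 1 single-agent patients who added azacitidine, and when.
2. Add Phase 1 single-agent summaries of TEAEs, worst-grade laboratory shifts, maximum QTcF and exposure, cut the day before the first azacitidine dose.
3. Show data from the first azacitidine dose onward in a separate column and listing for single agent followed by combination.
4. Keep the uncut tables alongside, so that both views are available.

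The cost is SAP wording, one derived date and one extra column. The SAP allows changes until database lock, and after that the same tables can be reported as a documented deviation. The downside is that a late FT-2102 toxicity appearing after the switch leaves the cut column. It remains visible in the extra column and in the uncut tables.
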